2. LIST OF ABBREVIATIONS

AE	adverse event
ALT	alanine transaminase
ARR	annualized relapse rate
AST	aspartate transaminase
BID	twice daily
BUN	blood urea nitrogen
CNS	central nervous system
CRO	contract research organization
DHA	Directions for Handling and Administration
DMF	dimethyl fumarate
eCRF	electronic case report form
EDSS	Expanded Disability Status Scale
GCP	Good Clinical Practice
GI	gastrointestinal
ICF	informed consent form
ICH	International Council for Harmonisation
IDMC	Independent Data Monitoring Committee
IV	intravenous
IVMP	intravenous methylprednisolone
LLN	lower limit of normal
MMF	monomethyl fumarate
MRI	magnetic resonance imaging
MS	multiple sclerosis
PK	pharmacokinetics
PTH	parathyroid hormone
RRMS	relapsing-remitting multiple sclerosis
SABR	Safety and Benefit-Risk Management
SAE	serious adverse event
SUSAR	suspected unexpected serious adverse reaction
TID	3 times daily
ULN	upper limit of normal
US	United States
WBC	white blood cell

CONFIDENTIAL

The information contained herein may not be used, disclosed, or published without the written consent of
Biogen MA Inc.

3. SYNOPSIS

Protocol Number:	109MS311
Protocol Title:	A Multicenter Extension Study to Determine the Long-Term Safety and Efficacy of BG00012 in Pediatric Subjects With Relapsing-Remitting Multiple Sclerosis
Version Number	3.0
Name of Study Treatment:	BG00012 (Dimethyl Fumarate; Tecfidera®)
Study Indication:	Relapsing-remitting multiple sclerosis (RRMS)
Study Rationale	With no approved multiple sclerosis (MS) therapies in the pediatric population, there exists a significant unmet need for approved treatment options. In the adult population, BG00012 is a therapeutic option with demonstrated efficacy and acceptable tolerability and safety profiles combined with the ease of oral administration. BG00012 was first approved (as Tecfidera) in the United States in 2013 for the treatment of adult patients with relapsing forms of MS and has since been approved in Europe and other regions. This study will extend therapy from the ongoing BG00012 pediatric Study 109MS202, in which the pharmacokinetics and efficacy of BG00012 in pediatric subjects with RRMS are being evaluated, in order to further evaluate the long-term safety and efficacy of BG00012 in these subjects.
Phase of Development:	3
Study Objectives and Endpoints:	
The primary objective of the study is to evaluate the long-term safety of BG00012 in subjects who completed Study 109MS202.
 
The primary endpoint that relates to this objective is the incidence of adverse events (AEs), serious AEs, and discontinuations of study treatment due to an AE
 
Secondary objectives and endpoints are as follows:
 
To evaluate the long-term efficacy of BG00012.
 
• The total number of new or newly enlarging T2 hyperintense lesions on brain magnetic

CONFIDENTIAL

The information contained herein may not be used, disclosed, or published without the written consent of
Biogen MA Inc.

resonance imaging scans

- The annualized relapse rate
- The proportion of subjects who experience 1 or more relapses during the study period

To describe the long-term MS outcomes in subjects who completed Study 109MS202.

- The degree of disability as measured by the Expanded Disability Status Scale (EDSS) and disability progression (as measured by at least a 1.0-point increase on the EDSS from baseline EDSS ≥ 1.0 that is sustained for 24 weeks or at least a 1.5-point increase on the EDSS from baseline EDSS = 0 that is sustained for 24 weeks)

Study Design:

This is a multicenter, open-label extension of Study 109MS202 that is designed to evaluate the long-term safety and efficacy of BG00012 in pediatric subjects.

Study Location:

Approximately 20 sites globally are planned.

Number of Planned Subjects:

The number of subjects who are eligible for this study will be determined by the number of subjects who have completed Study 109MS202 as per protocol.

Study Population:

This study will be conducted in subjects who completed Study 109MS202 as per protocol.

Detailed criteria are described in Section 8.

Treatment Groups:

All subjects will receive BG00012 240 mg twice daily (2 capsules of 120 mg).

Duration of Treatment and Follow-up:

The treatment period is 96 weeks (2 years) and the Follow-Up Safety Visit will take place 4 weeks after the last dose of study treatment.

[figure not shown]
CONFIDENTIAL

The information contained herein may not be used, disclosed, or published without the written consent of Biogen MA Inc.

4. STUDY SCHEMATIC AND SCHEDULE OF ACTIVITIES FOR STUDY 109MS311

4.1. Study Schematic

Figure 1: Study Design

CONFIDENTIAL

The information contained herein may not be used, disclosed, or published without the written consent of Biogen MA Inc.

4.2. Schedule of Activities

Table 1: Study Activities for Study 109MS311

Tests and Assessments ¹	Year 1						Year 2					Safety Follow-Up Visit
	Baseline Visit (Day 1) ²	Visit 1 (Week 12±5d)	Visit 2 (Week 16±5d)	Visit 3 (Week 24±5d)	Visit 4 (Week 36±5d)	Visit 5 (Week 48±5d)	Visit 6 (Week 60±5d)	Visit 7 (Week 64±5d)	Visit 8 (Week 72±5d)	Visit 9 (Week 84±5d)	Visit 10 (Week 96±5d)	
Informed Consent and Assent ³	X											
Eligibility Criteria	X											
Medical History	X											
MS-Related Medical History ⁴	X											
Physical Examination	X											X
Body Weight	X	X		X	X	X			X	X	X	X
Height	X			X		X			X		X	X
Vital Signs ⁵	X	X		X	X	X	X		X	X	X	X
12-Lead ECG	X										X	X
Hematology	X	X		X	X	X	X		X	X	X	X
Blood Chemistry	X	X		X	X	X			X		X	X
Urine Pregnancy Test ⁶	X	X		X	X	X			X	X	X	X
Urinalysis ^{7,8}	X	X		X	X	X			X		X	X
PTH and Vitamin D Levels	X					X					X	X
Brain MRI Scan ^{9,10}	X		X	X				X	X			
EDSS	X	X		X	X	X			X		X	
Dispense Study Treatment ¹¹	X	X		X	X	X	X		X	X		
Concomitant Therapy and Procedures Recording	Monitor and record throughout the study											
AE/SAE Reporting	Monitor and record throughout the study											

AE = adverse event; ECG = electrocardiogram; EDSS = Expanded Disability Status Scale; MRI = magnetic resonance imaging; MS = multiple sclerosis;
PTH = parathyroid hormone; SAE = serious adverse event.

¹ Tests and assessments must be completed prior to study treatment dispensation.

CONFIDENTIAL

The information contained herein may not be used, disclosed, or published without the written consent of Biogen MA Inc.

² The Final Study Visit for Study 109MS202 will serve as the Baseline Visit for this extension study. The Final Study Visit from Study 109MS202 can be within 4 weeks of the Baseline Visit for Study 109MS311 if the 2 visits cannot be combined.

³ Written informed consent from the subject's parents or legal guardians and assent from the subject, if appropriate, must be obtained prior to performing any study-related procedures.

⁴ MS-related medical history will include complete MS history of disease, MS diagnostic criteria, MS signs and symptoms, and MS treatment history.

⁵ Vital signs include body temperature, pulse rate, and systolic/diastolic blood pressure measurements.

⁶ For females of childbearing potential. Results must be known prior to study treatment dispensation.

⁷ Urine cytology must be performed at all visits indicated if a subject experiences hematuria (of unknown etiology) at 2 consecutive visits. If urine cytology is positive for malignant cells, the subject must permanently discontinue study treatment.

⁸ Study treatment must be temporarily withheld or permanently discontinued if any of the laboratory values meet the criteria defined in the protocol.

⁹ MRI must not be performed within 30 days of receiving a course of steroids.

¹⁰The time between the Week 24 MRI and the Week 16 MRI must be the same as the time between the Day 0 MRI and Week -8 MRI in Study 109MS202 within a window of ± 3 days. For example, if the Day 0 and Week -8 MRIs for a particular subject occurred 8 weeks apart in Study 109MS202, then the Week 24 MRI in Study 109MS311 should be 8 weeks ± 3 days after the Week 16 MRI. If necessary, the Week 24 MRI may be conducted separately from the Week 24 clinic visit. Similarly, the time between the Week 72 MRI and the Week 64 MRI must be the same as the time between the Day 0 MRI and Week -8 MRI in Study 109MS202 within a window of ± 3 days. If necessary, the Week 72 MRI may be conducted separately from the Week 72 clinic visit.

¹¹Initial dispensation of study treatment may require an additional visit on or around Day 7. Laboratory results must be evaluated and eligibility confirmed prior to dispensation of study treatment.

CONFIDENTIAL

The information contained herein may not be used, disclosed, or published without the written consent of Biogen MA Inc.

Table 2: Additional Study Activities for Study 109MS311

Tests and Assessments	Unscheduled Relapse Assessment Visit ¹ (within 72 hours after symptom onset)	Discontinuation/ Withdrawal Visit ² (as soon as possible but no later than 4 weeks after last dose of study treatment)	Lymphocyte Follow-Up Visit ³
Physical Examination	X	X	X
Body Weight	X	X	X
Height		X	
Vital Signs ⁴	X	X	X
12-Lead ECG		X	
Hematology ^{5,6}	X	X	X
Blood Chemistry ⁶	X	X	
Urine Pregnancy Test ⁷	X	X	
Urinalysis ^{6,8}	X	X	
PTH and Vitamin D Levels		X	
EDSS	X	X	
Brain MRI Scan ⁹		X ¹⁰	
Relapse Assessment	X		
Concomitant Therapy and Procedures		Monitor and record throughout the study	
AE/SAE Recording		Monitor and record throughout the study	

AE = adverse event; ECG = electrocardiogram; EDSS = Expanded Disability Status Scale; LLN = lower limit of normal; MRI = magnetic resonance imaging; MS = multiple sclerosis; PTH = parathyroid hormone; SAE = serious adverse event.

¹ An Unscheduled Relapse Assessment Visit will be conducted within 72 hours of symptom onset of a suspected relapse (i.e., new or recurrent neurologic symptom[s]).

² Discontinuation refers to discontinuation of study treatment. Withdrawal refers to withdrawal of subjects from the study. The Discontinuation/Withdrawal Visit should be conducted as soon as possible and no later than 4 weeks after the last dose of study treatment.

CONFIDENTIAL

The information contained herein may not be used, disclosed, or published without the written consent of Biogen MA Inc.

³ Subjects who complete, temporarily withhold, or permanently discontinue study treatment for any reason and have a lymphocyte count <LLN will continue protocol-required visits and assessments and be followed every 4 weeks for 24 weeks and then every 3 months (**unless clinically indicated more often or at the Investigator's discretion**) until the lymphocyte count is \geq LLN or for 52 weeks after the last dose, or until one of the following occurs: 1) the subject continues on commercial BG00012 following study withdrawal/completion, or 2) the subject is initiated on another MS disease-modifying therapy. Note: lymphocyte counts \geq LLN at 2 consecutive visits are required.

⁴ Vital signs include body temperature, pulse rate, and systolic/diastolic blood pressure measurements.

⁵ Hematology testing must be performed every 4 weeks in subjects with lymphocyte count <LLN.

⁶ Study treatment must be temporarily withheld or permanently discontinued if any of the laboratory values meet the criteria defined in the protocol.

⁷ For females of childbearing potential.

⁸ Urine cytology must be performed if a subject experiences hematuria (of unknown etiology) at 2 consecutive visits or at the Unscheduled Relapse Assessment Visit or the Discontinuation/Withdrawal Visit.

⁹ An MRI must not be performed within 30 days of receiving a course of steroids.

¹⁰ A brain MRI scan will be performed unless assessed in the last 30 days.

CONFIDENTIAL

The information contained herein may not be used, disclosed, or published without the written consent of Biogen MA Inc.

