7.2.2. Treatment

Eligible subjects will report to the study site to receive study treatment approximately every 12 weeks for up to 96 weeks (2 years).

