10. DISCONTINUATION OF STUDY TREATMENT AND/OR WITHDRAWAL OF SUBJECTS FROM THE STUDY

10.1. Discontinuation of Study Treatment

A subject *must* permanently discontinue BG00012 for any of the following reasons:

- The subject becomes pregnant. Study treatment must be discontinued immediately. Report the pregnancy according to the instructions in Section [15.4.1](#).
- The subject experiences a medical emergency that necessitates permanent discontinuation of study treatment.
- The subject has lymphocyte count $<500/\text{mm}^3$ for 6 months as outlined in [Table 4](#) and [Table 5](#).
- The subject experiences a protocol-specified change in laboratory values that necessitates permanent discontinuation of treatment as outlined in [Table 3](#) and [Table 4](#).
- The subject cannot tolerate study treatment.
- The subject receives any of the disallowed concomitant medications for this study.
- The subject or subject's parent/legal guardian desires to discontinue treatment.
- At the discretion of the Investigator for medical reasons or for noncompliance.

The reason for discontinuation of study treatment must be recorded in the subject's eCRF.

Subjects who discontinue treatment may remain in the study and continue protocol-required tests and assessments.

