15.5. Contraception Requirements

Sexually active subjects of reproductive potential must practice effective contraception during the study and for at least 30 days after their last dose of study treatment. Investigators should advise subjects of the potential risks associated with pregnancy while taking BG00012 and on the appropriate use of contraceptives (as defined below).

CONFIDENTIAL

The information contained herein may not be used, disclosed, or published without the written consent of Biogen MA Inc.

For the purposes of the study, highly effective contraception is defined as use of 1 or more of the following:

For females:

- Established use of oral, injected, or implanted hormonal methods of contraception.
- Placement of an intrauterine device or intrauterine system.
- Barrier methods of contraception with use of a spermicide: condom or occlusive cap (diaphragm or cervical/vault caps) with spermicidal foam/gel/film/cream suppository. The use of barrier contraceptives should always be supplemented with the use of a spermicide (where approved/applicable).
- Female surgical sterilization (e.g., bilateral tubal ligation).

For males:

- Effective male contraception includes the use of condoms with spermicide.

True abstinence, when this is consistent with the preferred and usual lifestyle of the subject, can be considered an acceptable method of contraception based on the evaluation of the Investigator who should also take into consideration the duration of the clinical trial. Periodic abstinence (e.g., calendar, ovulation, symptothermal, or postovulation methods) and withdrawal are not considered acceptable methods of contraception.

Pregnancy reporting is described in Section [15.4.1](#).

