19.3. Changes to Final Study Protocol

Protocol modifications that affect subject safety, the scope of the investigation, or the scientific quality of the study must be approved by the ethics committee before implementation of such modifications to the conduct of the study. If required by local law, such modifications must also be approved by the appropriate regulatory agency prior to implementation.

However, Biogen may, at any time, amend this protocol to eliminate an apparent immediate hazard to a subject. In this case, the appropriate regulatory authorities will be notified subsequent to the modification.

In the event of a protocol modification, the ICF may require corresponding modifications (see Section 17).

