4.2. Schedule of Activities

Table 1: Study Activities for Study 109MS311

Tests and Assessments ¹	Year 1						Year 2					Safety Follow-Up Visit
	Baseline Visit (Day 1) ²	Visit 1 (Week 12±5d)	Visit 2 (Week 16±5d)	Visit 3 (Week 24±5d)	Visit 4 (Week 36±5d)	Visit 5 (Week 48±5d)	Visit 6 (Week 60±5d)	Visit 7 (Week 64±5d)	Visit 8 (Week 72±5d)	Visit 9 (Week 84±5d)	Visit 10 (Week 96±5d)	
Informed Consent and Assent ³	X											
Eligibility Criteria	X											
Medical History	X											
MS-Related Medical History ⁴	X											
Physical Examination	X											X
Body Weight	X	X		X	X	X			X	X	X	X
Height	X			X		X			X		X	X
Vital Signs ⁵	X	X		X	X	X			X	X	X	X
12-Lead ECG	X										X	X
Hematology	X	X		X	X	X			X	X	X	X
Blood Chemistry	X	X		X	X	X			X		X	X
Urine Pregnancy Test ⁶	X	X		X	X	X			X	X	X	X
Urinalysis ⁷⁸	X	X		X	X	X			X		X	X
PTH and Vitamin D Levels	X					X					X	X
Brain MRI Scan ⁹¹⁰	X		X	X				X	X			
EDSS	X	X		X	X	X			X		X	
Dispense Study Treatment ¹¹	X	X		X	X	X	X		X	X		
Concomitant Therapy and Procedures Recording	Monitor and record throughout the study											
AE/SAE Reporting	Monitor and record throughout the study											

AE = adverse event; ECG = electrocardiogram; EDSS = Expanded Disability Status Scale; MRI = magnetic resonance imaging; MS = multiple sclerosis; PTH = parathyroid hormone; SAE = serious adverse event.

¹ Tests and assessments must be completed prior to study treatment dispensation.

CONFIDENTIAL

The information contained herein may not be used, disclosed, or published without the written consent of Biogen MA Inc.

² The Final Study Visit for Study 109MS202 will serve as the Baseline Visit for this extension study. The Final Study Visit from Study 109MS202 can be within 4 weeks of the Baseline Visit for Study 109MS311 if the 2 visits cannot be combined.

³ Written informed consent from the subject's parents or legal guardians and assent from the subject, if appropriate, must be obtained prior to performing any study-related procedures.

⁴ MS-related medical history will include complete MS history of disease, MS diagnostic criteria, MS signs and symptoms, and MS treatment history.

⁵ Vital signs include body temperature, pulse rate, and systolic/diastolic blood pressure measurements.

⁶ For females of childbearing potential. Results must be known prior to study treatment dispensation.

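### Week 60 is the only one of eight dispensing visits with no urine pregnancy test scheduled, which leaves 24 weeks between scheduled tests

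*Protocol*

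**What the plan says.** Protocol Section 7.2.2 sets the dispensing rhythm: "Eligible subjects will report to the study site to receive study treatment approximately every 12 weeks". In Table 1 of Section 4.2 (v3.0) this becomes eight dispensing visits, at Day 1 and Weeks 12, 24, 36, 48, 60, 72 and 84.

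The urine pregnancy test row of the same table is marked at Day 1, at Weeks 12, 24, 36, 48, 72, 84 and 96, and at the Safety Follow-Up Visit. It is blank at Weeks 16, 60 and 64. Footnote 6 to that row reads "For females of childbearing potential. Results must be known prior to study treatment dispensation".

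Section 10.1 lists pregnancy first among the reasons for mandatory permanent discontinuation: "The subject becomes pregnant. Study treatment must be discontinued immediately".

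Two other provisions bear on the point. Section 15.5 requires contraception: "Sexually active subjects of reproductive potential must practice effective contraception during the study". Table 2 adds a pregnancy test at the discontinuation/withdrawal visit and at the relapse visit ("An Unscheduled Relapse Assessment Visit will be conducted within 72 hours of symptom onset of a suspected relapse"), but not at lymphocyte follow-up visits.

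**The concern.** The scheduled test is the protocol's routine check that a subject is not pregnant before more drug is issued. At Week 60 that check is missing. Roughly 12 weeks of drug, enough to reach Week 72, goes out with no scheduled result since Week 48.

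If footnote 6 governs every dispensation, the table and its footnote disagree and the Week 60 cell was probably left out. If it governs only the tests that the row schedules, there is no contradiction, but the wording is ambiguous and the long interval remains.

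What is at stake is the length of an undetected fetal exposure in an adolescent population. No estimate, test or analysis population in the SAP depends on it.

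**Working it through.** This is a count and an interval check. The documents state no maximum interval between pregnancy tests, so there is no planned figure to reproduce.

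**Inputs.** The dispensing row and the urine pregnancy test row of protocol v3.0 Table 1, read across its 12 visit columns, and the ±5-day window on each scheduled visit after Day 1. Safety Follow-Up is taken at 4 weeks after Week 96 (Section 7.2.3).

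| Visit | Drug dispensed | Test scheduled | Weeks since last scheduled test |
|---|---|---|---|
| Day 1 | yes | yes | – |
| Week 12 | yes | yes | 12 |
| Week 16 | no | no | |
| Week 24 | yes | yes | 12 |
| Week 36 | yes | yes | 12 |
| Week 48 | yes | yes | 12 |
| **Week 60** | **yes** | **no** | **12, not tested** |
| Week 64 | no | no | |
| Week 72 | yes | yes | 24 |
| Week 84 | yes | yes | 12 |
| Week 96 | no | yes | 12 |
| Safety Follow-Up | no | yes | 4 |

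**Coverage.** 8 dispensing visits, 7 with a test; the exception is Week 60.

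**Intervals.** The eight tests from Day 1 to Week 96 give seven intervals: 12, 12, 12, 12, 24, 12 and 12 weeks. In days:

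- Week 48 to Week 72: 24 × 7 = 168, with ±5 at each end, so 158 to 178.
- A 12-week interval between two windowed visits: 12 × 7 = 84, ±10, so 74 to 94.
- Day 1 to Week 12, with a window at one end only: 84 ± 5, so 79 to 89.

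**Worst-case exposure before the next scheduled test.** For a conception just after the Week 48 test, it is about 24 weeks as the schedule stands and about 12 weeks with a test at Week 60.

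**With the test added at Week 60.** Coverage becomes 8 of 8. The intervals become 12 weeks eight times over, then 4 weeks to Safety Follow-Up.

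**Is the blank consistent with the rest of the schedule?**

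- Footnote 1 already puts tests before dispensing. Footnote 6 adds something further, "Results must be known prior to study treatment dispensation", which reads most naturally as a condition on issuing drug. The matching footnote in Table 2, where no dispensing is listed, omits that sentence.
- Week 84 is the other reduced dispensing visit in Year 2. It drops height, chemistry, urinalysis and EDSS but keeps the pregnancy test.
- In superseded v1.0, all eight dispensing visits (Day 1, Weeks 16, 24, 36, 48, 64, 72 and 84) had a test, and the longest interval was 16 weeks. The Week 64 visit carried body weight, vital signs, hematology and the pregnancy test.
- In superseded v2.0, dispensing moved from Week 16 to Week 12 and from Week 64 to Week 60. The pregnancy test followed the drug to Week 12. None of the four Week 64 checks followed it to Week 60.
- In v3.0, vital signs and hematology appear at Week 60. The pregnancy test does not.

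The history is supporting context only. The gap is visible in v3.0 alone.

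**The case against.** The strongest case against accepts the reading of the table but disputes its weight.

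**Risk.** Section 5.3.1 reports no nonclinical findings of teratogenicity. Inclusion criterion 3 requires contraception of all females of childbearing potential, and exclusion criterion 7 bars those considering pregnancy. Section 15.6.1 makes investigators monitor and record pregnancies. Nothing stops an investigator from testing at Week 60. The 24-week exposure is a worst case, and the number of subjects at risk cannot be derived. All of this stands and lowers the expected harm. None of it requires a result at Week 60, and Section 10.1 still demands immediate discontinuation. Because the protocol schedules a test at every other dispensing visit, it does not rely on contraception alone.

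**Intent.** v3.0 edited the Week 60 column and left the test out, which could be a deliberate choice of a limited visit. No section sets a 12-week maximum, and v1.0 allowed 16 weeks. So an oversight is likely but not proven, and departing from a superseded version is not in itself an error. Still, the documents give no reason for treating Week 60 differently from Week 84.

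**Footnote 6.** On its broad reading, sites must already obtain a result at Week 60. That reading supports adding the mark, because a site working from the table would not know to do the test.

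**SAP.** SAP Section 3, Table 1 has the same blank but appears to follow v2.0: it shows neither vital signs nor hematology at Week 60. It is not independent confirmation of v3.0.

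**Timing.** The documents do not show how many subjects had yet to reach Week 60, so the practical benefit of an amendment depends on when it is made.

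**Conclusion.** The concern holds. In the current protocol, one of eight dispensing visits has no scheduled urine pregnancy test, and the Week 48 to Week 72 interval is 24 weeks (158 to 178 days), twice the 12 weeks between every other pair of consecutive on-treatment tests.

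The reading of the table is secure: the row accounts for all 12 visit columns, and v2.0 shows the same blank. Whether the omission was intended is not known, and the conclusion does not depend on it.

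The 24-week exposure figure assumes conception just after Week 48, no recognition of the pregnancy, no relapse or discontinuation visit, no ad hoc test, and continued dosing. The claim is limited to scheduled tests. This is a modest safety-monitoring gap that should be closed because closing it is cheap. It does not threaten any of the trial's conclusions.

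**What to change.** In protocol Section 4.2, Table 1, mark the urine pregnancy test at Visit 6 (Week 60). Reword footnote 6 to say that a result is needed before each dispensation. Mirroring the mark in SAP Section 3, Table 1 keeps the documents aligned but changes no analysis.

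The cost per subject is one urine test, for females of childbearing potential only, at a visit already attended for vital signs, hematology and dispensing. The administrative cost is larger. Under Section 19.3, changes affecting subject safety "must be approved by the ethics committee before implementation of such modifications", and about 20 sites are planned. The change is best bundled with the next amendment and is worth making only while some subjects have yet to reach Week 60.
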